Clinical Study Protocol

CCP-020 (Diacerein 1%) Topical Ointment

Sponsor Protocol No. CCP-020-105

TKL Study No. PB710217

**A 6-Week, Randomized Study to Evaluate the Potential of
CCP-020 (Diacerein 1%) Topical Ointment
to Induce a Photoallergic Skin Reaction
in Healthy Subjects, Using a Controlled Photopatch Test Design**

Author:

[REDACTED]

Document type:

Clinical Study Protocol

Development Phase:

1

Document Date:

25-October-2017

Document Status

Final v1.0

Number of Pages:

43

Property of **Castle Creek Pharmaceuticals, LLC.**

Confidential

May not be used, divulged, published, or otherwise disclosed
without the consent of **Castle Creek Pharmaceuticals, LLC.**

Synopsis

Study Title:	A 6-Week, Randomized Study to Evaluate the Potential of CCP-020 (Diacerein 1%) Topical Ointment to Induce a Photoallergic Skin Reaction in Healthy Subjects, Using a Controlled Photopatch Test Design
TKL Study Number:	PB710217
Sponsor Protocol Number:	CCP-020-105
Sponsor:	Castle Creek Pharmaceuticals, LLC
Development Phase:	1
Study Objectives:	To determine the potential of CCP-020 (Diacerein 1%) Topical Ointment to induce a photoallergic skin reaction using a controlled photopatch testing procedure.
Study Design:	During the 3-week Induction Phase, CCP-020 (Diacerein 1%) Topical Ointment and vehicle ointment, will each be applied 2 times per week (Monday and Thursday) to 2 sites on the infrascapular area of the back under fully occlusive patch conditions for approximately 24 hours (± 4 hours). Minimal erythema dose (MED) irradiation will also be performed for each subject on Day 1. After patch removal, all application sites will be evaluated and one application site of each study product will be irradiated with 2 times the subject's MED using the full Xenon lamp spectrum. All sites will be evaluated at approximately 48 hours later when irradiated on Tuesdays and 72 hours later when irradiated on Fridays. An additional application of study product may be applied on the Monday of rest week 4 if the subject misses an irradiation session during the induction phase of the study. At Challenge, CCP-020 (Diacerein 1%) Topical Ointment and vehicle ointment will each be applied once to 2 naive sites on the infrascapular area of the back under fully occlusive patch conditions for approximately 24 hours (± 4 hours). After patch removal, all application sites will be evaluated and one site of each test product will be irradiated with 6 J/cm^2 of Ultraviolet A (UVA) followed by 0.5 times the subject's MED of UVA/Ultraviolet B (UVB). An additional untreated site will also be irradiated at Challenge and will serve as an untreated control. Each site, including the untreated control site, will be evaluated again at approximately 24 hours (± 4 hours), 48 hours (± 4 hours), and 72 hours (± 4 hours) following irradiation. A Rechallenge will be performed if a cutaneous response observed during the Challenge Phase indicates possible photosensitization or at the discretion of the Investigator.
Planned Sample Size:	50 evaluable subjects
Study Population:	Healthy adult male and female volunteer subjects
Investigational Products:	CCP-020 (Diacerein 1%) Topical Ointment Vehicle Ointment
Control:	An untreated irradiated non-occlusive (open) control site.
Efficacy Evaluation Criteria:	Not applicable

Safety Evaluation Criteria: The safety endpoints for this study are irritation responses during the Induction Phase, positive responses at Challenge (i.e., reactions indicative of a sensitization response) and adverse events. All local and systemic adverse events (AEs) observed by or reported to the Investigator will be evaluated. The intensity, duration, and causal relationship to the study products are to be rated for all AEs.

Statistical Methods: The focus of the statistical analysis will be the comparison with controls of the photoallergic response to the study products. The diagnosis of photosensitization response will be made by the Investigator based on review of the observed skin responses after Challenge.

Mean numerical equivalent scores, including all scores assigned during Induction, will be analyzed with analysis of variance (ANOVA) with factors subject and treatment. All pairwise treatment comparisons will be performed. Pairs to be compared are: each test sample irradiated versus non-irradiated and all pairwise comparisons on each side.

Number of Study Centers: Single Center

Planned Date of Study December 2017 – February 2018

Signature page

[figure not shown]
Product names: **CCP-020 (Diacerein 1%) Topical Ointment**
Vehicle Ointment

TKL Study number: **PB710217**

Sponsor protocol number: **CCP-020-105**

The signatures of the following representatives constitute their approval of this protocol and provide the necessary assurances that this study will be conducted according to all stipulations stated in the protocol, including all statements as to confidentiality. It is also agreed that the study will not be initiated without the approval of an appropriate Institutional Review Board.

Approved by the following:

[figure not shown]
Signature page for the Principal Investigator

Product names: **CCP-020 (Diacerein 1%) Topical Ointment**
Vehicle Ointment

TKL Study number: **PB710217**

Sponsor protocol number: **CCP-020-105**

I have read this protocol and agree to conduct this study in accordance with all stipulations of the protocol and in accordance with the Declaration of Helsinki.

Investigators and study administrative structure

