3.4.5.2. Blinding

CCP-020 (Diacerein 1%) topical ointment, vehicle ointment, and control will not be blinded to investigative personnel involved in the preparation/application and removal of treatments.

Investigative personnel who are involved in the preparation/application and removal of the treatments will be unblinded and will not perform the evaluation of skin responses. The subjects and the trained evaluator who will be evaluating skin responses will be blinded to IPs and the treatment allocation; however, because of the demarcations/skin coloration remaining on the skin following patch removal, complete blinding of the evaluators cannot be completely assured.

Investigative personnel who are blinded, including the Investigator and trained evaluator involved in the evaluation of responses, will remain blinded during the course of the study until Database Lock and finalization of the Statistical Analysis Plan (SAP).

In the event of an emergency, if possible, the Investigator or designee will contact the Sponsor with notification of the intent to unblind the treatment codes prior to the actual unblinding. If it is not possible to notify the Sponsor prior to the unblinding, the Investigator or designee will contact the Sponsor immediately following the unblinding procedure and follow with a written notification to document the exact manner in which the code was broken and the justification for the unblinding. The Investigator will communicate the treatment identification to only the investigative personnel who require the information to manage the emergency. Unblinding will happen on site at TKL.

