4. STATISTICAL METHODS

4.1. General Considerations for Data Analysis

The focus of the statistical analysis will be the comparison with controls of the photoallergic response to the study products. The diagnosis of photosensitization response will be made by the Investigator based on review of the observed skin responses after Challenge.

The mean score by subject and treatment, including all scores assigned during Induction, will be analyzed in the analysis of variance with factors subject and treatment. All pairwise treatment comparisons will be performed.

All statistical processing will be performed using the SAS® system (version 9.2 or higher). No interim or subgroup analyses are planned.

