4.3. Subject Populations for Analysis

All subjects who receive treatment will be evaluable for AEs. The evaluation of photosensitization will be based on all subjects who complete the Challenge Phase of the study. Subjects who completed Challenge are those who have received at least 6 applications/irradiation of study products, and at least 11 subsequent evaluations during Induction, completed the Rest Phase and have received one application of study products at Challenge, subsequent irradiation and at least 4 evaluations (3 post-irradiation evaluations) for that product. The analysis of local tolerability (photo irritation) will be based off all subjects who complete the Induction Phase of the study. Subjects who completed Induction are those who have received at least 6 applications/irradiation of study products, and at least 11 subsequent evaluations during Induction.

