4.6. Safety Evaluation

4.6.1. Assessment of Responses

All assigned scores during Induction and Challenge will be summarized by frequency counts by time point and treatment. The incidence of reactions will be summarized by frequency counts for each treatment. The mean score by subject and treatment, including all scores assigned during Induction, will be analyzed using Fisher's least significant differences in the analysis of variance (ANOVA) with factors subject and treatment. All pairwise comparisons will be performed: CCP-020 (Diacerein 1%) topical ointment on both the irradiated and non-irradiated sides, and vehicle ointment on both the irradiated and non-irradiated sides.

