4.6.2. Photosensitivity

The determination of dermal photosensitization potential will be made by the Investigator based on specific scoring criteria derived from observations in the Challenge Phase of the study and confirmed in the Rechallenge Phase, if necessary. The incidence of photosensitization reactions will be summarized by frequency counts for each treatment. If photosensitization occurs, the 95% confidence interval for the proportion of subjects with photosensitization for each product will be calculated. Photosensitivity will not be determined by statistical methods.

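### The Induction photo-irritation analysis plans only pairwise comparisons; if CCP-020 irritates without light and irradiation itself reddens skin, no single pair isolates the light-dependent drug effect

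*Combined protocol and SAP*

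**What the plan says.** Each subject carries both products on both sides of the back, and one side is irradiated at 2 times the subject's MED after each Induction patch (Section 3.1). Each subject's mean score over all Induction readings, per condition, is then analysed.

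- **Synopsis, Statistical Methods:** ANOVA with subject and treatment as factors. "Pairs to be compared are: each test sample irradiated versus non-irradiated and all pairwise comparisons on each side". For two products this gives four pairs.
- **Section 4.1:** the same two factors. "All pairwise treatment comparisons will be performed".
- **Section 4.6.1:** Fisher's "least significant differences in the analysis of variance (ANOVA) with factors subject and treatment". It continues: "All pairwise comparisons will be performed: CCP-020 (Diacerein 1%) topical ointment on both the irradiated and non-irradiated sides, and vehicle ointment on both" sides. Four conditions give six pairs.
- **Section 4.3:** "The analysis of local tolerability (photo irritation) will be based off all subjects who complete the Induction Phase of the study".
- **Section 4.6.2:** the only planned confidence interval is for the proportion of subjects photosensitized. It adds: "Photosensitivity will not be determined by statistical methods".

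No section names a product-by-irradiation term, or an estimate, SE, test or interval for the difference of differences. Sections 4.7 and 4.9 add no methods. Section 3.4.5.2 refers to an SAP still to be finalised; no separate SAP text was available for this review.

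**The concern.** Photo-irritation means irritation that the drug causes because light is present. By Section 3.5.3 the MED is the exposure that just produces erythema, so twice that dose may redden skin under any product, including an inert one. An irradiated versus non-irradiated difference within CCP-020 therefore mixes the light-dependent drug effect with plain UV erythema. The irradiated CCP-020 versus vehicle difference removes the UV part but keeps any irritation the drug causes in the dark.

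The design collects what is needed to remove both, since every subject supplies all four conditions, but the plan does not combine them. A reader of the report could see several significant pairs and still not know whether light makes the drug more irritating. Section 3.5.7.1 does separate contact from light-dependent reactions for the photosensitivity assessment, by comparing irradiated and non-irradiated sites on Rechallenge. The Induction statistics have no counterpart.

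**Working it through.** **1. What each pair estimates.** Let m be the vehicle non-irradiated mean, d the irritation CCP-020 causes without light, u the rise from UV alone, and g the light-dependent drug effect. The cell means are:

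| | Non-irradiated | Irradiated |
|---|---|---|
| Vehicle | m | m + u |
| CCP-020 | m + d | m + d + u + g |

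| Comparison | Estimates |
|---|---|
| CCP-020, irradiated − non-irradiated | u + g |
| Vehicle, irradiated − non-irradiated | u |
| Irradiated side, CCP-020 − vehicle | d + g |
| Non-irradiated side, CCP-020 − vehicle | d |
| CCP-020 irradiated − vehicle non-irradiated (Sections 4.1 and 4.6.1 only) | d + u + g |
| CCP-020 non-irradiated − vehicle irradiated (Sections 4.1 and 4.6.1 only) | d − u |
| Difference of differences (not planned) | g |

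If d and u are both non-zero, no pair equals g. If d = 0, the irradiated-side pair equals g.

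**2. Precision under the planned model.** There is no figure in the plan to reproduce: it gives no SD, effect size, alpha or power for this ANOVA, and the 50 subjects rest on convention (Section 4.2). With n = 50, four conditions and residual SD s:

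- Residual df = (4 − 1)(50 − 1) = 147; two-sided 5% (assumed) gives t = 1.976.
- Pair: SE = s√(2/50) = 0.200s; 95% half-width = 0.395s.
- Contrast: SE = s√(4/50) = 0.283s; 95% half-width = 0.559s.
- SE ratio = √2 = 1.41.
- Effect detectable with 80% power: 0.56s for a pair, 0.80s for the contrast.

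**3. Paired analysis in grades.** Assume independent site errors with SD w, and a UV reactivity that is the same at a subject's two irradiated sites, so that it cancels. The contrast has SE = 2w/√50 and the irradiated-side pair has SE = √2·w/√50, each with 49 df (t = 2.01). For an effect of 0.2 grade:

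| w (assumed) | Contrast SE | Half-width | Contrast power | Irradiated-pair power (paired form, d = 0) |
|---|---|---|---|---|
| 0.2 | 0.057 | 0.11 | 93% | about 100% |
| 0.3 | 0.085 | 0.17 | 64% | 90% |
| 0.5 | 0.141 | 0.28 | 28% | 50% |

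If UV reactivity instead varies independently between the two irradiated sites with SD 0.4, then at w = 0.3 the contrast SD is √(4 × 0.09 + 2 × 0.16) = 0.82, the SE is 0.117, and power falls from 64% to about 39%.

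**4. Do the pairs tell the two situations apart?** Simulated trials used n = 50, unbounded scores, d = 0.3–0.5 and u = 0.5–1.0 grade, all assumed. At site SD 0.2–0.3 the Synopsis's four pairs were all significant in 98–100% of trials, both at g = 0 and at g = 0.2. The paired contrast rejected toward photo-irritation in 2–3% at g = 0.

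**5. Where the contrast is weak.** With integer 0–3 scores (site SD 0.3, UV SD 0.2), vehicle non-irradiated scores near the floor (mean 0.13) and d = 0.2–0.5, the contrast rejected falsely in 10–28% of trials. With that mean at 0.33 the figure was 4–8%. Near the ceiling (d = 0.5, u = 2) its power fell to 15%. These bounded-score figures rest on one simulation of 1,000 trials per scenario and are indicative only.

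**6. Related conflicts in the text.**

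| | Synopsis and Section 3.1 | Section 3.5.7.1 |
|---|---|---|
| Irradiation of the untreated site | Described for Challenge: "An additional untreated site will also be irradiated at Challenge and will serve as an untreated control" (Section 3.2 likewise) | Described for Induction and Challenge together |
| Induction readings after irradiation | About 48 h (Tuesdays) or 72 h (Fridays) | About 24, 48 and 72 h |

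Table 2 footnote d also mentions irradiating the untreated site; where its marker belongs is uncertain in the extracted table.

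**The case against.** The strongest reply is that the difference of differences is not this protocol's estimand. The objective is photoallergic potential, judged by the Investigator at Challenge. The Induction endpoint is irritation, and for tolerability the planned pairs are natural simple effects: the drug with light, the drug without light, and light within each product. The vehicle pair shows the UV effect directly. If the non-irradiated pair shows no drug irritation, the irradiated pair answers the question with more power. The point estimate of g is also one subtraction away, and the contrast is least reliable at the floor when plain irritation is present.

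Most of this stands, and it is why the contrast belongs beside the pairs and not in their place. What remains is the case with both d and u non-zero. Section 4.3 itself calls the analysis one of photo-irritation, and no interval is planned for that quantity. A non-significant non-irradiated pair also does not establish that d is zero.

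Stronger readings that a reader might infer, and that the documents do not support:

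- *The plan would wrongly declare photo-irritation in nearly every trial.* No decision rule is attached to the pairs, so the 98–100% is not an error rate of the plan.
- *The photoallergy conclusion is compromised.* Section 4.6.2 keeps that outside statistical testing.
- *The final analysis will omit the contrast.* The separate SAP was not available, so this cannot be said.
- *It is unclear whether untreated-site scores enter the ANOVA comparisons.* Section 4.6.1 names only the four product conditions.

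On reading times, the 11 Induction evaluations in Section 4.3 can be reached under Section 3.1 as 6 at patch removal plus 5 after irradiation. That does not remove the conflicting wording.

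**Conclusion.** The point holds in a limited form, as an inexpensive improvement worth considering. The planned pairs do not isolate the light-dependent drug effect when CCP-020 irritates without light and the irradiation causes erythema by itself. They can do so when the drug does not irritate in the dark. That conclusion follows from the cell means and needs no assumed numbers.

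How much the contrast would help depends wholly on assumed SDs and effects, because the documents give none. The power figures also assume that UV reactivity is common to a subject's two irradiated sites, and they are optimistic if it is not. The contrast takes g on an additive scale, which a short ordinal score may not respect near either end. The consequence is confined to the Induction irritation endpoint.

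**What to change.** In Section 4.6.1, keep the planned pairs and add as a supportive result the per-subject contrast (CCP-020 irradiated − CCP-020 non-irradiated) − (vehicle irradiated − vehicle non-irradiated). Report its estimate and 95% CI from a paired analysis, and carry it into the SAP. Add two statements:

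- An irradiated versus non-irradiated difference within one product is not by itself evidence of photo-irritation.
- The contrast assumes additivity and is to be read with the score frequencies already planned in Section 4.6.1 when scores lie near the floor or ceiling.

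The cost is one contrast and two sentences, with no new data or visits. The drawbacks are a wider interval and lower power than a pair, and possible false rejection near the floor.

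Separately, the sponsor should reconcile Section 3.5.7.1 and Table 2 footnote d with the Synopsis and Sections 3.1 and 3.2 on when the untreated site is irradiated, and Section 3.5.7.1 with the Synopsis and Section 3.1 on Induction reading times.

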1. INTRODUCTION

This study evaluates the potential of CCP-020 (Diacerein 1%) Topical Ointment to induce a photoallergic skin reaction using a controlled photopatch test design. Because CCP-020 (Diacerein 1%) Topical Ointment is formulated for topical use, it is necessary to determine the potential of this product to cause a photoallergic reaction after application to the skin.

The study will be conducted in compliance with Food and Drug Administration (FDA) regulations, the ethical principles of the Declaration of Helsinki concerning medical research in humans (Recommendations Guiding Physicians in Biomedical Research Involving Human Subjects, Helsinki 1964 and amendments 2013), the International Conference on Harmonization (ICH) – Good Clinical Practice (GCP) Guidelines as currently amended, and all applicable standard operating procedures (SOPs) of TKL Research, Inc. (TKL).

1.1. Background Information

CCP-020 (previously developed as AC-203) is a topical ointment containing diacerein (4,5-bis[acetoxy]-9,10-dihydro-9,10-dioxo-2-anthracene carboxylic acid; also known as diacetyl-rhein), a highly purified anthraquinone derivative, and is being developed by Castle Creek Pharmaceuticals for the treatment of epidermolysis bullosa simplex (EBS). The capsule formulation of diacerein, intended for oral use and systemic absorption, was initially approved for use in osteoarthritis (OA) in France in 1992 (as Artodar[®], ART50[®], or Zondar[®]). Since then, it has received marketing authorization in over 30 countries in Europe, South America, and Asia. It is classified as a Symptomatic Slow-Acting Drug in OA. Following oral administration of the capsule formulation, diacerein is rapidly metabolized to the deacetylated active metabolite, rhein. Similarly, diacerein in the topical formulation is hydrolyzed to rhein in the epidermis and the dermis following administration. Diacerein and rhein have been shown to inhibit the in vitro and in vivo production and activity of interleukin (IL)-1 β and other proinflammatory cytokines. It has a novel mode of action that differentiates it from non-steroidal anti-inflammatory drugs (NSAIDs) and other conventional forms of drug therapy.

For the development of CCP-020, a total of 10 animal studies have been conducted with CCP-020 ointment 1%, including one skin penetration study, three acute dermal toxicity studies, one phototoxicity study, three pharmacokinetic studies, and two sub-chronic juvenile toxicity studies. CCP-020 was well-tolerated in these studies and no untoward adverse effects (AEs) were noted. To date, two clinical studies of CCP-020 have been completed in patients with epidermolysis bullosa simplex (EBS). These include a Phase one pilot study in five patients and a Phase 2, multiple-site study in 17 patients in Europe. The Phase 2 study demonstrated CCP-020 was well-tolerated and no treatment-related AEs were reported. The Investigator's Brochure should be consulted for summaries of the results of these studies.¹

This Phase 1 study will assess the photoallergic potential of CCP-020 (Diacerein 1%) topical ointment.

2. STUDY OBJECTIVES

The objective of this study is to determine the photoallergic potential of CCP-020 (Diacerein 1%) topical ointment when topical application to skin is followed by light exposure.

In addition, safety will be assessed by evaluation of any adverse events (AEs) reported during the study.

3. INVESTIGATIONAL PLAN

3.1. Study Design

This will be a randomized, double-blind, single-center, vehicle-controlled, within-subject comparison study of the study products, CCP-020 (Diacerein 1%) topical ointment, vehicle ointment, and an untreated irradiated non-occluded (open) control site. A total of 4 application sites (2 cm x 2 cm each) will be marked on the subject's back and distributed so that 2 sites are on each side of the back. One side of the back will be designated for irradiation after approximately 24 hours (± 4 hours) of study product application and the other side will remain non-irradiated. An additional site will be marked on the "irradiated side" of the back. The site will receive no study product, but will be irradiated at Challenge to serve as an untreated irradiated non-occluded control.

A defined area (approximately 50 cm²) on the infrascapular region of each subject's back will be irradiated to determine the minimal erythema dose (MED) of ultraviolet (UV) light.

During the 3-week Induction Phase, 0.2 mL of each study product will be applied to 2 sites twice each week (Monday and Thursday) for approximately 24 hours (± 4 hours) under occlusive patch conditions (6 applications). After patch removal, all application sites will be evaluated and one application site of each study product will be irradiated with 2 times the subject's MED using the full Xenon lamp spectrum. The sites will be evaluated by a trained evaluator. All sites will be reevaluated post irradiation, at approximately 48 hours later when irradiated on Tuesdays and at approximately 72 hours later when irradiated on Fridays except when irradiated on the last Friday of the Induction Phase or if a subject is taking a missed visit during induction, the sites will not be evaluated. These procedures will be performed each week for 3 weeks of the Induction Phase. Dermal reactions at the application sites will be evaluated using a visual scale that rates the degree of erythema, edema, and other signs of cutaneous irritation (see [Table 3](#) and [Table 4](#)).

At the end of the Induction Phase, the subjects will enter a Rest Period of 10-17 days and then a Challenge Phase. One application/irradiation session may be missed during the Induction Phase. It must be made-up during Week 4. An additional application of study product may be applied on the Monday of rest week 4 if the subject had missed an irradiation session during the induction phase of the study. In either case, no evaluation will be required following irradiation.

At Challenge, each study product will be applied in an amount of 0.2 mL to 2 naive sites once for approximately 24 hours (± 4 hours) under occlusive patches. After 24 hours (± 4 hour) of product application, all sites will be evaluated and one application site of each product and the additional untreated control site will be irradiated. The sites will be examined for dermal reactions at approximately 24 hours (± 4 hours), 48 hours (± 4 hours), and 72 hours (± 4 hours) post-irradiation. A Rechallenge will be performed if a cutaneous response observed during the Challenge Phase indicates possible photosensitization or at the discretion of the Investigator.

The safety endpoints for this study are irritation responses during the Induction Phase, positive responses at Challenge (i.e., reactions indicative of a sensitization response) and adverse events.

